Subjects will be closely monitored for treatment-related adverse events during all infusions. For the initial ABT-414 infusion, pre infusion vital signs should be taken and direct observation is required for the first 15 minutes of the infusion. Also for the initial ABT-414 infusion, subjects must remain at the site for monitoring for 60 minutes post-infusion. For subsequent infusions, post-infusion monitoring is not required; however, pre-infusion vital signs should still be taken. Longer observation periods and more frequent vital sign checks may be required in subjects who experience infusion reactions.

Recommendations for dose reductions (either as required by protocol or at the discretion of the investigator) are as follows: For a current dose of 1.5 – 2.0 mg/kg, it is recommended that the dose be reduced by 0.5 mg (or more, at the investigators discretion). For a current dose of 0.75 – 1.25 mg/kg, it is recommended that the dose be reduced by 0.25 mg (or more, at the investigators discretion).

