The ABT-414 (active and placebo) will be provided as a lyophilized powder in vials. Each 100 mg vial of ABT-414 and placebo will be reconstituted with 5.0 mL of sterile water for injection to provide a 20 mg/mL ABT-414 active or a placebo solution. Each 20 mg vial of ABT-414 and placebo will be reconstituted with 1.0 mL of sterile water for injection to provide a 20 mg/mL ABT-414 active or a placebo solution. The ABT-414 is dosed as a fixed dose [or] based on body weight. The contents of two or more reconstituted vials may be diluted to accomplish the desired dose. The total volume administered will be dependent upon the assigned dose for that dosing period and/or the tolerability of the ABT-414/placebo. The

ABT-414 and placebo solution(s) will be administered via intravenous (IV) infusion. Specific dose preparation and documentation details will be provided to the site pharmacy outside of this protocol.

Guidelines for ABT-414 dose preparation, volume, and rate of infusion will be supplied by AbbVie to study site staff, within the study manual.

The dosing schedule for the hepatic impairment sub-study can be found in [Appendix IX](#).

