8.1.1 Dose Modifications for ABT-414/Placebo

For all observed toxicities, subjects should be assessed for inter-current illness or other causes and treated as appropriate.

Starting doses and suggested dose level reductions are shown in [Table 9](#), and subsequent subsections discuss when dose reductions should be considered or are required. More aggressive dose reductions are always allowed if the Investigator believes that it is in the best interest of the subject.

With the exception of ophthalmologic toxicities as described in [Section 8.1.2](#) and hepatic laboratory abnormalities as described in [Section 8.1.6](#), all dose reductions are permanent unless a toxicity initially attributed as potentially related to ABT-414/placebo is later re-attributed as not potentially related and discussed with the Neuro-Medical Oncology study chair, AbbVie Medical Monitor or their designee.

Table 9. ABT-414/Placebo Dose Modification Table during Chemoradiation and Adjuvant Phase

Dose Level	Dose	
	Chemoradiation Phase	Adjuvant Phase
Starting Dose	2.0 mg/kg	1.25 mg/kg*
1 st Reduction	1.5 mg/kg	1.0 mg/kg
2 nd Reduction	1.0 mg/kg	0.75 mg/kg
3 rd Reduction	-	0.5 mg/kg
	-	Discontinue

* If CTCAE Grade 3 eye toxicity is observed during the Chemoradiation Phase, then 1.0 mg/kg is recommended, but not required, as the starting dose for the Adjuvant Phase.

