8.1.6 Hepatic Laboratory Abnormalities (ABT-414/Placebo)

Guidelines for ABT-414/placebo dose modifications related to hepatic laboratory abnormalities are presented in [Table 11](#).

Table 11. ABT-414/Placebo Dose Modification Guidelines for Hepatic Laboratory Abnormalities

Hepatic Laboratory Abnormality	ABT-414/Placebo
ALT or AST > 5 × ULN* but ≤ 20 × ULN (and TBL ≤ 2 × ULN)	
 • Hold drug regardless of assessed relationship to drug. See Section 8.4 for guidelines on repeat testing (ALT, AST, ALP, TBL) and evaluation. • Dosing may not be resumed until ALT and AST have recovered to ≤ 5 × ULN* • Dosing may be resumed at the same dose if ALT or AST was elevated >5 × ULN* for less than 2 weeks. Additionally, dosing may be resumed at the same dose if another likely cause has been identified. • Dosing must be resumed at a reduced dose (see Table 9)** if ALT or AST was elevated > 5 × ULN* for more than 2 weeks and no other likely cause has been identified. • Following dose reduction, if ALT and AST remain ≤ 5 × ULN* after 2 doses at the reduced dose level, then re-escalation to the previous dose is allowed at the investigator's discretion. • If a subsequent dose reduction is required due to hepatic laboratory abnormalities, then re-escalation is not allowed.
ALT or AST > 20 × ULN or ALT or AST > 3 × ULN and TBL > 2 × ULN	
Hold drug regardless of assessed relationship to drug. See Section 8.4 for guidelines on repeat testing (ALT, AST, ALP, TBL) and evaluation.
 
If another clear cause has been identified, drug may be resumed when ALT and AST ≤ 5 × ULN and TBL ≤ 2 × ULN
 
In general, if no other cause has been identified, drug should be permanently discontinued, and rechallenge not attempted.
 
Rechallenge can be considered after consultation with the sponsor if all of the following are met:
 
 • the subject has shown important benefit from the drug and other options are not available, • ALT and AST have recovered to ≤ 5 × ULN and TBL has recovered to ≤ 2 × ULN, • the subject has been informed of the potential risk and has consented to the rechallenge, • close follow-up of the subject is feasible.

ALP = alkaline phosphatase, ALT = alanine transferase, AST = aspartate transferase, TBL = total bilirubin

* If elevated at baseline, either 5 × the baseline value or 8 × ULN, whichever is lower.

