APPENDIX IX. SUBJECTS WITH MILD TO MODERATE HEPATIC IMPAIRMENT

This appendix outlines the ABT-414 sub-study in subjects with hepatic impairment. The revised schedule of assessments for the hepatic impairment sub-study is provided in [Table 3H](#) below.

Sub-Study Objective

To assess the pharmacokinetics, safety and tolerability of ABT-414 in subjects with newly diagnosed *EGFR*-amplified GBM who have mild or moderate hepatic impairment.

Overview

This is a Phase 1, open-label, multicenter sub-study. Approximately 6 subjects with mild hepatic impairment and 6 subjects with moderate hepatic impairment will be enrolled if they meet all inclusion criteria and do not meet any of the exclusion criteria.

All subjects with hepatic impairment will be assigned to active treatment with ABT-414 during the Chemoradiation and Adjuvant Phases of treatment. Radiation therapy and TMZ therapy will be administered to hepatically impaired subjects the same way as those with normal hepatic function. The pharmacokinetics of TMZ in patients with mild-to-moderate hepatic impairment have been shown to be similar to those observed in normal hepatic function. Caution should only be exercised when TMZ is administered to patients with severe hepatic impairment. The visit schedule and study procedures will be the same as for other study subjects unless described otherwise in this appendix.

After meeting the selection criteria for subjects with hepatic impairment, as shown below, approximately 6 subjects will be assigned to each of the two cohorts according to their hepatic function as shown in [Table 1H](#). Within each cohort, the first 3 subjects will be assigned to dose level 1. If the dose level 1 was tolerated, the subsequent subjects may be assigned to dose level 2.

Table 1H. Cohorts of Subjects with Hepatic Impairment and Treatment

Cohorts	Hepatic Function	Dose Level	Chemoradiation Phase	Adjuvant Phase (Cycles 1 – 2)	Maintenance Phase (Cycle 3 and After)
A	Child-Pugh A	1a	1.0 mg/kg	1.0 mg/kg	1.0 mg/kg
		2	2.0 mg/kg	1.25 mg/kg	1.25 mg/kg
B	Child-Pugh B	1b	1.0 mg/kg	0.5 mg/kg	1.0 mg/kg
		2	2.0 mg/kg	1.25 mg/kg	1.25 mg/kg

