PK – Antidrug Antibody	0 hour (pre-dose)	0 hour (pre-dose)					

Radiation Therapy and Temozolomide Administration

Radiation therapy and temozolomide therapy will be administered as described in the main protocol.

ABT-414 Administration

At the Screening Visit, all subjects will be assigned a unique subject number that will indicate the subject is enrolling into the open label hepatic impairment sub-study. The subjects in this sub-study will be stratified by their Child-Pugh scores (mild or moderate impairment) as described in [Table 2H](#).

Subjects will receive ABT-414 by IV infusion over 30 – 40 minutes once every 2 weeks during the Chemoradiation Phase (on Day 1 of Weeks 1, 3, and 5 of the 6-week regimen) and during the

Adjuvant Phase (on Day 1 and Day 15 of each 28-day cycle for 12 cycles). If, after completing 12 cycles of ABT-414 in the Adjuvant Phase, the subject is tolerating the drug and the Investigator believes the subject is continuing to benefit from ongoing ABT-414 treatment, the Adjuvant Phase may be extended following consultation with the Neuro-Medical Oncology Chair. ABT-414 will continue according to the same dosing schedule at the discretion of the Investigator as long as disease progression has not been determined.

The mg/kg dose for each dose will be as described in [Table 1H](#). The mg/kg dose will be determined from the weight on Day 1 of the Chemoradiation Phase and need not change during subsequent treatment unless there is a weight change by more than 10% from baseline. Recalculation of dose for < 10% weight changes is allowed at the discretion of the Investigator. There will be no cap on the weight of the subject or on the number of milligrams administered for overweight subjects.

If TMZ treatment is discontinued due to intolerance during either the Chemoradiation Phase or Adjuvant Phase, subjects will continue receiving ABT-414 infusions according to the same study schedule.

ABT-414 Toxicity Management and Individual Subject Dose Modifications

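### Appendix IX prints ABT-414 reduction steps in mg for doses given in mg/kg; read literally, the recommended minimum step is under 1% of the dose

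*Protocol*

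**What the plan says.** Appendix IX ends with a paragraph on reducing ABT-414 in individual sub-study subjects. It applies both to reductions the protocol requires and to those the investigator chooses. It has two dose bands:

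- Current dose 1.5 to 2.0 mg/kg: "2.0 mg/kg, it is recommended that the dose be reduced by 0.5 mg (or more, at the investigators discretion".
- Current dose 0.75 to 1.25 mg/kg: "1.25 mg/kg, it is recommended that the dose be reduced by 0.25 mg (or more, at the investigators discretion".

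In both sentences the current dose carries "/kg" and the step does not.

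Elsewhere the sub-study doses by weight. The administration text in the same appendix says "The mg/kg dose for each dose will be as described in" Table 1H, and every entry in that table is in mg/kg. It also says "There will be no cap on the weight of the subject or on the number of milligrams administered for overweight subjects". The main protocol's ladder, Table 9 in Section 8.1.1, is in mg/kg too: 2.0, 1.5, 1.0 for chemoradiation and 1.25, 1.0, 0.75, 0.5 for the adjuvant phase.

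On who starts where, the Appendix IX overview says "Within each cohort, the first 3 subjects will be assigned to dose level 1". In Table 1H, dose levels 1a and 1b both start chemoradiation at 1.0 mg/kg.

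**The concern.** A reduction in mg cannot be set against a dose in mg/kg without a body weight, and at any ordinary adult weight the printed step is negligible. The paragraph is an operative dosing instruction. The Appendix IX overview keeps main-study procedures only where the appendix does not say otherwise, and here it does say otherwise.

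The subjects concerned have liver disease, and the interim summary in Protocol Section 1.0 lists raised ALT, AST and GGT among the events more frequent on ABT-414. If the step were applied literally, a subject could be documented as dose-reduced while exposure was essentially unchanged. Safety and pharmacokinetic data from dose level 1 also inform whether and how dose level 2 proceeds, so a nominal reduction could mislead that decision.

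Table 9 does not cover every case. Its chemoradiation column stops at 1.0 mg/kg, which is where level 1a and 1b subjects start. Table 11 in Section 8.1.6 says "Dosing must be resumed at a reduced dose (see Table 9") when ALT or AST stays above its threshold for more than two weeks with no other likely cause. For these subjects during chemoradiation, that reference leads to no lower dose, and Appendix IX is the only text with a numeric step.

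**Working it through.** **Inputs**

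- Steps and dose bands: Appendix IX, as above.
- Main-study dose levels: Table 9, Section 8.1.1.
- Concentration after reconstitution: 20 mg/mL (Section 5.4: "reconstituted with 5.0 mL of sterile water for injection to provide a 20 mg/mL ABT-414 active").
- Body weight: not given in the documents. Assumed 50, 70 and 100 kg.

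**1. Do the printed numbers match the protocol's own ladder?**

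Differences between successive Table 9 levels:

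- Chemoradiation: 2.0 − 1.5 = 0.5 and 1.5 − 1.0 = 0.5 mg/kg.
- Adjuvant: 1.25 − 1.0 = 0.25, 1.0 − 0.75 = 0.25 and 0.75 − 0.5 = 0.25 mg/kg.

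These are the Appendix IX numbers, in the same dose bands, with "/kg" attached. Read as mg, the printed steps do not give this ladder.

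**2. Size of the step under each reading**

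Read as mg, share of dose = step / (dose × weight). Read as mg/kg, share of dose = step / dose.

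| Current dose (mg/kg) | Step | As mg, 50 kg | As mg, 70 kg | As mg, 100 kg | As mg/kg |
|---|---|---|---|---|---|
| 2.0 | 0.5 | 0.50% | 0.36% | 0.25% | 25% |
| 1.5 | 0.5 | 0.67% | 0.48% | 0.33% | 33% |
| 1.25 | 0.25 | 0.40% | 0.29% | 0.20% | 20% |
| 1.0 | 0.25 | 0.50% | 0.36% | 0.25% | 25% |
| 0.75 | 0.25 | 0.67% | 0.48% | 0.33% | 33% |

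For example, at 2.0 mg/kg and 70 kg: 0.5 / (2.0 × 70) = 0.5 / 140 = 0.36%.

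**3. Does the conclusion depend on the assumed weight?**

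The literal step equals 1% of the dose when weight = step / (0.01 × dose):

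- 1.5 mg/kg with 0.5 mg, or 0.75 mg/kg with 0.25 mg: 33.3 kg.
- 2.0 mg/kg with 0.5 mg, or 1.0 mg/kg with 0.25 mg: 25 kg.
- 1.25 mg/kg with 0.25 mg: 20 kg.

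Above 33.3 kg the step is under 1% at every listed dose. Widening the assumed range to 40–120 kg gives 0.17% to 0.83%.

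**4. Volume at 20 mg/mL**

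- Literal: 0.5 / 20 = 0.025 mL and 0.25 / 20 = 0.0125 mL.
- In mg/kg at 70 kg: 0.5 × 70 = 35 mg, or 1.75 mL; 0.25 × 70 = 17.5 mg, or 0.875 mL.

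**5. Subjects for whom Table 9 has no lower chemoradiation dose**

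Three subjects in each of two cohorts start at dose level 1: 3 × 2 = 6 of about 12 planned. With "/kg" restored, Appendix IX gives them 1.0 − 0.25 = 0.75 mg/kg.

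**The case against.** The strongest reply is that this is a slip that would harm nobody. The step is only a recommendation, with a larger one left to the investigator. Taking 0.5 mg off a dose of about 140 mg (2.0 mg/kg at 70 kg) is implausible on its face, and a pharmacist asked to withhold 0.025 mL would probably query it. About 12 open-label subjects are planned, and SAP Section 6.0 excludes them from the main analysis population. All of that stands and limits the consequences.

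Other text also helps the reader:

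- Section 8.1.1 permits more aggressive reductions, and Section 6.1 sets a withdrawal floor at 0.5 mg/kg. Neither gives a step.
- Table 9's adjuvant column goes from 1.0 to 0.75 mg/kg, and its footnote also works in mg/kg: after Grade 3 eye toxicity during chemoradiation, "then 1.0 mg/kg is recommended, but not required, as the starting dose for the Adjuvant Phase". This shows the intent, but it is not an instruction for chemoradiation.
- Table 11 waives its reduction when the next planned dose is already lower. That can help level 1b, which falls to 0.5 mg/kg in adjuvant cycles 1–2. It does not help level 1a, which stays at 1.0 mg/kg, or either level for a further chemoradiation dose.
- Appendix X refers subjects who continue after the interim analysis to Section 8.0, which holds the correct ladder. This may narrow current exposure, but Appendix X does not name sub-study subjects and does not correct Appendix IX.

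The reply therefore reduces the likely harm without making the printed instruction right.

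**Conclusion.** The concern holds. Appendix IX contains a unit error in both reduction sentences, and the intended values can be recovered from the protocol itself. As printed, the minimum recommended step is 0.20% to 0.67% of the dose at 50 to 100 kg, against an intended 20% to 33%. The exact percentages rest on assumed weights; the finding that the step is below 1% needs only a weight above 33.3 kg. That "/kg" was dropped is an inference, but a strong one, since the numbers and bands coincide with Table 9 and nothing in the documents supports a sub-milligram step.

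It should be corrected because it is a live dosing instruction for subjects with liver disease. It has no bearing on the main trial's power, type I error or efficacy analyses.

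**What to change.** In the last paragraph of Appendix IX, change the two steps to 0.5 mg/kg and 0.25 mg/kg, after the sponsor's clinical team confirms that these are intended. If any site is still dosing sub-study subjects under Appendix IX, which the documents do not say, notify it of the correction; a short clarification to sub-study sites would be enough.

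The textual change is "/kg" added twice in one paragraph. The remaining cost is issuing the clarification or carrying the edit in an amendment. No analysis, sample size or SAP text changes.

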APPENDIX X SUBJECTS CONTINUING PARTICIPATION AFTER MAIN STUDY

This appendix outlines the modifications to the study procedures and ABT-414 dosing in subjects who are currently receiving ABT-414 and who choose to continue ABT-414 treatment after the results from the pre-planned interim efficacy analysis. Subjects who received placebo will be discontinued from the study.

At the time of the interim efficacy analysis, there were approximately 48 subjects who remained on active ABT-414 treatment. The RTOG Steering Committee and AbbVie determined it was appropriate to allow subjects who are receiving ABT-414 to continue doing so based on investigator and subject decision.

Requirements for continuing treatment with ABT-414 after interim efficacy analysis

1. If the subject was receiving blinded treatment, they must be confirmed to be receiving ABT-414.
2. Must voluntarily sign and date the updated informed consent form, approved by an Independent Ethics Committee (IEC)/Institutional Review Board (IRB)

Study Activities

Only study activities necessary for study drug dosing, safety monitoring and adverse event reporting will be continued. The revised schedule of study assessments for these subjects is provided in [Table 2b](#) below.

Table 2b. Study Activities	28-Day Cycles ^a				Final Study Drug Visit ^d /At Progression	35-Day F/U ^e	49-Day F/U
	Day 1 of Every Cycle (1, 2, 3 etc.)	Day 1 of Odd-Numbered Cycles (1, 3, 5, etc.)	Day 15 of Every Cycle ^b	Day 22 of Every Cycle ^c			
Symptom-directed Physical Exam	X ^f		X ^f				
Ophthalmology Exam		X ^g				X ^g	X ^g
Chemistry	X				X	X	
Hematology	X			X	X	X	
Adverse Event Assessment/Concomitant Medications	X		X		X	X	X ^k
Temozolomide Administration	X ^h						
ABT-414 Administration	X ⁱ		X ⁱ				
Prophylactic Eye Drop Administration	X ^j		X ^j				

F/U = Follow-up

- a. Assessments will be based on 28-day treatment cycles, with the first cycle starting approximately 4 weeks after completion of radiation therapy. Subjects will receive concomitant TMZ and study drug (ABT-414) for the first 6 cycles, and study drug monotherapy for an additional 6 cycles or until disease progression or study drug discontinuation.
- b. Day 15 visit will not be performed after discontinuation of study drug (ABT-414) treatment.
- c. As per TMZ prescribing information, during the 28-day cycle of TMZ, a blood count for ANC and platelets should be performed 21 days (\pm 2 days) after the start of each TMZ cycle. If the ANC falls below 1,500/ μ L or if the platelet count falls below 100,000/ mm^3 , then blood counts should be performed weekly until recovery to these levels before TMZ dosing. A certified local lab may be used instead of central lab; if so, ANC and platelet results should be reported in the eCRF. Day 22 testing may be omitted for cycles in which TMZ is not administered or if local prescribing information allows for a different testing schedule for ANC and platelets.
- d. Final Study Drug Visit to be performed approximately 14 days after last dose of ABT-414.
- e. To be performed 35 days (\pm 3 days) after the last dose of study drug (ABT-414). If the Final Study Drug Visit is more than 35 days after the last dose of study drug, then 35-day safety follow-up procedures will not be performed.
- f. Physical exams will be performed only as needed for safety management and adverse event reporting.
- g. Ophthalmology exams will be performed only as needed for safety management and AE/SAE reporting. The last ophthalmology exam following discontinuation of ABT-414 may be done at the 35-Day F/U or 49-Day F/U Visit. Targeted ophthalmology exam data will not be collected by the Sponsor.
- h. TMZ will be administered once daily on Days 1 through 5 of each 28-day cycle for 6 cycles per the local prescribing information.
- i. ABT-414 infusion will be administered on Day 1 and Day 15 of each 28-day cycle for 12 cycles.
- j. Prophylactic eye drops will be administered daily for 7 days with each dose of ABT-414, from 2 days before until 4 days after each dose of study drug (ABT-414), as described in Section 5.5 of the main study. Patients will receive management of ocular side effects as per investigator discretion. In this case, ABT-414 dose interruption and/or reduction may be used, and any available prophylactic or supportive care measures may be employed without restriction, at the discretion of the investigator.
- k. If the subject is unable to return to the site for the Day 49 Follow Up Visit, a phone call may be conducted to obtain AE/SAE and concomitant medication information.

ABT-414 Administration and Individual Subject Discontinuation

ABT-414 will be administered as described in the main protocol.

Subjects may continue receiving ABT-414 while drug supply is available as long as disease progression has not been determined.

ABT-414 Toxicity Management and Individual Subject Dose Modifications

Section 8.0 of the main protocol provides guidance for toxicity management and dose modifications.

Adverse Events and Concomitant Medications

[figure not shown]
Adverse event and concomitant medication data will be collected to support regulatory safety reporting requirements.

APPENDIX XI PROTOCOL AMENDMENT: LIST OF CHANGES

[figure not shown]
Title Page

"Investigator:"

"Neurosurgery" previously read:

[figure not shown]
Has been changed to read:

[figure not shown]
Title Page

"Investigator:"

"Statistician" previously read:

Has been changed to read:

Section 1.0 INTRODUCTION AND BACKGROUND**Subsection Additional Safety Information****Delete: last paragraph**

Taken together, the efficacy and safety data available to date demonstrate an acceptable benefit/risk profile of ABT-414 in patients with EGFR-amplified GBM (see Section 1.2) and support continued investigation of this investigational agent in the current trial.

Section 1.0 INTRODUCTION AND BACKGROUND**Subsection Summary of Results from Pre-planned Interim Efficacy Analysis****Add: new subsection title and text****Summary of Results from Pre-planned Interim Efficacy Analysis**

An interim efficacy analysis based on a data cut of 30 April 2019 was performed by the RTOG Independent Data Monitoring Committee (IDMC), at which time 346 OS events had been observed out of 639 subjects included in the main part of the study. The primary analysis of OS based on the Intent-to-Treat (ITT) population showed no difference in OS between groups, with a median OS of 18.9 vs. 18.7 months for ABT-414 and placebo, respectively. The weighted ($\rho = 0$, $\gamma = 0.2$) stratified log-rank test p-value (1-sided) was 0.628, and the observed hazard ratio (HR) (95% CI) for OS was 1.01 (0.82, 1.25). The median PFS was 8.0 vs. 6.3 months for ABT-414 and placebo, respectively, with a stratified log-rank test p-value (1-sided) of 0.029. The observed hazard ratio (HR) (95% CI) for PFS was 0.84 (0.70, 1.02). Preliminary analysis of demographic and clinical characteristics did not reveal any factors predictive of OS benefit for the addition of ABT-414 to standard RT/TMZ therapy.

Overall, 99.4% and 97.8% of subjects experienced at least 1 adverse event, and 87.3% and 62.3% experienced a Grade 3 or higher AE in the ABT-414 and placebo arms, respectively. Overall, 94.7% and 36.1% of subjects experienced at least 1 ocular adverse event related to corneal epitheliopathy, 61.0% and 0.6% experienced a Grade 3 or higher AE related to corneal epitheliopathy, and 11.8% and 0% discontinued study drug (ABT-414 or placebo) in the ABT-414 and placebo arms due to corneal epitheliopathy, respectively. The most common (> 10%) events related to corneal epitheliopathy included keratopathy, vision blurred, photophobia, dry eye, eye pain, keratitis, and punctate keratitis. Excluding events related to corneal epitheliopathy, events for which the incidence in the ABT-414 group was $\geq 5\%$ greater than in the placebo group included thrombocytopenia, gamma-glutamyltransferase increased, aspartate aminotransferase increased, alanine aminotransferase increased, constipation, blood alkaline

phosphatase increased, fatigue, and platelet count decreased. Excluding events related to corneal epitheliopathy, Grade 3 or higher events for which the incidence in the ABT-414 group was at least 5% and was $\geq 2\%$ greater than in the placebo group included thrombocytopenia, gamma-glutamyltransferase increased, and alanine aminotransferase increased.

The interim efficacy analysis results overall indicate no survival benefit for adding ABT-414 to standard RT/TMZ therapy in newly diagnosed GBM patients. However, given that no new important safety risks were identified, the RTOG Steering Committee and AbbVie believe it is appropriate to allow subjects who are currently receiving ABT-414 to continue ABT-414 treatment if the investigator and subject believe it is in the subject's best interest. For those subjects who choose to continue ABT-414, study procedures have been modified as described in Appendix X. The appendix provides guidance for study drug administration and collection of safety data related to AEs and SAEs. No additional efficacy data will be collected.

